**Fig. 2b** depicts the mean self-report CPD smoked (left axis, solid symbols) and expired CO levels obtained (right axis, empty symbols) at Baseline, 2-week and 1-month follow-up. Group R-E evidenced lower mean CPD than Group NR-E at both 2-week and 1-month follow-up (adjusted for baseline CPD, sex, years of regular smoking, and negative affect;  $p = 0.024$ ,  $d = 0.50$ ). Further, expired CO level was lower in Group R-E vs. NR-E at 1-month follow-up (adjusted for negative affect and race;  $p = 0.033$ ,  $d = 0.47$ ). Thus, the self-report smoking and CO findings indicate that RET confers a smoking reduction advantage over extinction training alone. Specifically, Group R-E evidenced a 25% greater reduction in smoking than group NR-E. **Fig. 3** depicts group level CPD smoked each day post-treatment. The figure clearly shows that RET had immediate effects on smoking and that the group difference persists unabated over the follow-up. In fact, this figure, together with the CO outcomes, suggests the possibility that the effect magnitude may be increasing during the latter 2-week period of follow-up. Lastly, there was trend level evidence that a greater percentage of participants in Group R-E (51.5%) vs. NR-E (25.6%) achieved a 60% reduction in smoking (from baseline) during follow-up (risk ratio (RR)=1.62 (0.98-2.67),  $p=.06$ ; At 2-week and 1-month follow-up time points, the  $p$ 's=.18 and .04, respectively)

We believe these results are very impressive, especially when one considers the modest difference in treatment between the two groups (i.e., a 5-minute smoking- vs. neutral-content

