- k) Participants must agree to forego any other medication or behavioral treatment for smoking cessation during their enrollment in this study (with the exception of a referral to the SC Quitline). Participants use of nicotine products such as e-cigs and nicotine patch will be

assessed over the course of the study). Additional treatment referrals will be provided at the end of the study.

- I) 20/20 vision with corrective lenses.

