
**x. Test Sessions:** Participants will complete seven follow-up test sessions: 24-hours, 2-weeks and 1-month, 6-weeks, 2-, 3- and 6-months. We use monetary compensation to minimize test session attrition (only 17.2% of participants did not complete the R21). Consistent with the R21 and Xue et al., 2012, each test sessions will involve a CR assessment identical to the baseline CR assessment described above except that a brief novel smoking picture cue sequence will also be presented. Importantly, some procedural elements will not occur in all test sessions. First, only the 24-hour follow-up test session will be performed under conditions of reinforced abstinence. The goal will be to assess the acute effects of the interventions under the same conditions of abstinence that occurred during the intervention. Participants will be encouraged to maintain their smoking abstinence at the conclusion of this session but will not be compensated for it (participants will be given a referral to the SC state Quitline, a free, anonymous service that supports abstinence). Second, for individuals randomized to the fMRI condition, the 24-hr test session is the only one in which an fMRI session (identical to the one in the baseline assessment) will be performed immediately after the initial CR assessment (cf., Fig. 6); those not assigned to the fMRI condition will remain in the CR laboratory and receive the same CR regimen as administered in the fMRI condition. Third, at the end of all but the 6-mo. test session, participants will receive a smoking diary in which to record the occurrence of both daily smoking and craving. A TLFB assessment of smoking behavior will be performed whenever diary data is not available; all but one of the R21 participants used their diary to collect smoking data as instructed. For those follow-up periods where more than 2-weeks elapse between visits (i.e., period between the 2 and 3 mo. follow-up visit and the period between the 3 and 6 mo. visit), study staff will phone contact participants every 2 weeks to collect diary data. Fourth, in all but the 24-hr. follow-up test session, expired CO and a saliva sample will be collected in order to biochemically corroborate, via CO and cotinine levels, self-report smoking/abstinence (salivary cotinine abstinence cutoff  $\leq$  15 ng/ml per SRNT Guidelines and CO abstinence cutoff  $\leq$  5 ppm). Assessment of the use of any nicotine products (e.g., e-cigarettes, dip, gum, patch) will be assessed at all follow-up visits. At study completion, debriefing will occur in which participant questions will be addressed and recommendations for additional cessation treatment will be provided.

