distributions). Overall statistical significance for the effects of treatment group, time, and their interaction will be assessed using a likelihood ratio test that compares the final model to a model consisting of an intercept term alone. The pre-specified hypothesis will be tested using model-based estimates to construct group comparisons across all the planned time points. Normality of residuals will be tested for models where appropriate and when found in error, appropriate transformations or non-parametric methods will be employed. Although mixed effects models have been proven highly efficient in cases where follow up data is missing at random, to accommodate other types of missing data, we will perform analyses using multiple imputation methods (Bayesian approach using both MCMC and FCS). The primary hypothesis associated with Aim 3 is that Group R-E will evidence decreased cue-elicited craving during follow-up testing. General linear mixed effects models will be constructed to assess group differences in craving over time. **Secondary Analysis:** Smoking relapse (i.e., days to 3 consecutive days of smoking ≥5 cigarettes) will be tested using a Cox Proportional Hazards regression model. Log-Log plots of the survival function and inclusion of a time variable treatment term will assess the proportionality assumptions and if models fail this assumption, a stratified Cox Regression model will be used. Also, we will measure end of study 7-day point prevalence abstinence as well as continuous abstinence using smoking diary/TLFB data. The effect of R-E training on abstinence outcomes will be tested using logistic regression models. **Biological Variables:** Exploratory analysis of sex effects on study outcomes will be assessed through main effects and the interaction between sex and study treatment assignment. Where significant interactions are found, sex stratified analyses will be conducted to assess the role of sex in the effect of RET on study outcomes. **Other secondary analyses** will assess i) differences between the control groups on main outcomes, ii) craving and cue reactivity differences during the three intervention sessions, and iii) the effects of treatment on ambient or background craving and cue reactivity (i.e., non-cue-elicited outcomes obtained early in test sessions). All analysis will be conducted using SAS/STAT v. 9.4 and Stata v. 14.

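### Section 12.0 defines abstinence from diary/TLFB data and never brings in the CO and cotinine cutoffs that section 10.0 sets for the follow-up visits

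*Combined protocol and SAP*

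**What the plan says.** Section 12.0 (Data Management, Secondary Analysis) gives the only operative definition of the abstinence outcomes: "we will measure end of study 7-day point prevalence abstinence as well as continuous abstinence using smoking diary/TLFB data". It continues: "The effect of R-E training on abstinence outcomes will be tested using logistic regression models". It names no biochemical criterion. Earlier in the same section, CPD and the indicator of a reduction of at least 60% are also taken from diary/TLFB data.

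Section 10.0, item x (Test Sessions), says that "in all but the 24-hr. follow-up test session, expired CO and a saliva sample will be collected in order to biochemically corroborate" self-reported smoking or abstinence. It states a "salivary cotinine abstinence cutoff" of at most 15 ng/ml and a "CO abstinence cutoff" of at most 5 ppm. The Design Overview (section 10.0, item i) and inclusion criterion h (section 5.0) state the same verification purpose, and criterion h extends it to changes in smoking.

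Two further passages bear on the point. Inclusion criterion k records other nicotine exposure ("Participants use of nicotine products such as e-cigs and nicotine patch will be" assessed during the study), and section 10.0, item x, repeats that assessment at all follow-up visits. In the background on the earlier R21 study (section 2.0, part B), biomarkers were analysed as an outcome: "expired CO level was lower in Group R-E vs. NR-E at 1-month follow-up" (p = 0.033, d = 0.47).

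**The concern.** The protocol plans the samples, states why they are taken and fixes the cutoffs, but the analysis section does not use them. An analyst following section 12.0 would classify a participant as abstinent from diary or TLFB data and would have no instruction to change that when CO or cotinine exceeds the cutoff.

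The plan also leaves several choices open:

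- whether CO and cotinine must both be met;
- what to do when they disagree;
- what a missing sample means;
- how to read cotinine in someone using e-cigarettes, gum or patch.

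Made after the data are seen, these choices could yield several different abstinence endpoints from one dataset.

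False reports of abstinence at the same rate in both arms shrink the observed group difference and cost power. A lesser consequence concerns the primary outcome. The R21 case for reduced smoking drew on self-report and CO together, yet this replication plans no biomarker analysis in support of CPD.

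**Working it through.** **Text check.** The mentions of CO, cotinine, saliva, diary/TLFB and abstinence, set against section 12.0:

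| Item | Where planned | Role in section 12.0 |
|---|---|---|
| Diary/TLFB | 10.0 item x | Source of CPD, 60% indicator, point prevalence and continuous abstinence |
| Expired CO, 2 weeks to 6 months | 10.0 item x, cutoff ≤ 5 ppm | None |
| Salivary cotinine, 2 weeks to 6 months | 10.0 items i and x, cutoff ≤ 15 ng/ml | None |
| Other nicotine product use | 5.0 criterion k; 10.0 item x | None |

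The follow-up visits concerned are 2 weeks, 1 month, 6 weeks, 2, 3 and 6 months; item x excepts the 24-hour test. CO is also checked at baseline and in the compensated-abstinence phase, but there it serves compliance and payment. The overnight criterion at baseline is ≤ 10 ppm (10.0 item viii), so the outcome definition has to name the follow-up cutoff explicitly.

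**No plan figure to reproduce.** The sample size section (10.0 item iii) treats CPD, the 60% reduction and craving. It gives no abstinence rate and no power for abstinence.

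**Illustration of equal misreporting.** All rates are assumptions. Let t be the true abstinence proportion in an arm and f the fraction of continuing smokers who report abstinence, the same in both arms.

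- Observed proportion: p = t + (1 − t)f. The risk difference is therefore multiplied by (1 − f).
- Two-sided pooled test of two proportions at 5%, with d = p₁ − p₂, s₀ = √[2p̄(1 − p̄)/n] and s₁ = √{[p₁(1 − p₁) + p₂(1 − p₂)]/n}.
- Power = 1 − Φ[(1.96s₀ − d)/s₁] + Φ[(−1.96s₀ − d)/s₁].
- n = 83 randomized or 62 completers per arm (10.0 item iii).

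Example, t = 0.25 vs 0.10, f = 0, n = 62: p̄ = 0.175, s₀ = 0.0682, s₁ = 0.0669. Then (0.1338 − 0.15)/0.0669 = −0.24, and power is 0.60.

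Example of the observed proportions at f = 0.05: 0.25 + 0.75 × 0.05 = 0.2875, and 0.10 + 0.90 × 0.05 = 0.145.

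| f | Observed R-E | Observed NR-E | Difference | OR | Power, n = 83 | Power, n = 62 |
|---|---|---|---|---|---|---|
| 0 | 0.2500 | 0.145 − 0.045 = 0.100 | 0.1500 | 3.0 | 72% | 60% |
| 0.05 | 0.2875 | 0.145 | 0.1425 | 2.4 | 61% | 49% |
| 0.10 | 0.3250 | 0.190 | 0.1350 | 2.1 | 51% | 40% |

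Range over other assumed true rates, for f = 0, 0.05 and 0.10:

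- 20% vs 10%: 44/34/28% at 83 and 34/27/22% at 62.
- 30% vs 15%: 64/55/47% at 83 and 52/44/37% at 62.

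The rows for 83 suppose that every randomized participant has a classified outcome. The comparison with f = 0 treats verified status as free of error, which flatters verification somewhat.

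**The case against.** The strongest reply is that this is one combined protocol and SAP. Item x already fixes abstinence cutoffs for corroboration, and section 12.0 names diary/TLFB as the data source because only daily records can cover a 7-day or continuous window. Nowhere does it say that a failed cutoff is to be ignored. Part of this stands: the biomarkers do have a stated role, and it would be wrong to say the plan collects them without purpose. But purpose and cutoffs are not a classification rule, and no other passage supplies one.

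It is also fair that abstinence is a secondary outcome without a power claim. H1, its secondary hypothesis and H3 do not concern it. In the R21, CPD differed by itself (p = 0.024) and CO was supportive. The biomarker model for CPD is therefore a worthwhile addition and does not correct an error.

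A reader might infer more: that participants know which video they saw, so false reporting will differ by arm and produce a false treatment effect. The documents do not support that. Both groups see the smoking video at baseline and receive the same extinction training. The consent text is not part of the public document, so what participants are told about the hypothesis is unknown. No misreporting rate is given for either arm. Unequal rates can be assumed: with 15% truly abstinent in both arms and false reporting of 10%, 15% or 20% against 5%, the test at 62 per arm rejects 9%, 20% or 37% of the time. Those results follow entirely from the chosen rates. Differential misreporting is a possible risk and is not established here.

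**Conclusion.** The point holds as a gap between two parts of the plan. CO and cotinine are collected at six visits, with cutoffs, to check self-report, while section 12.0 builds both abstinence outcomes from diary/TLFB data and uses the biomarkers in no outcome or analysis. Using samples already planned, with cutoffs already stated, is a cheap improvement that the sponsor should make.

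That conclusion rests on the text alone. Its numerical size is unknown. For assumed true rates of 25% vs 10%, equal false reporting by 5% or 10% of smokers costs about 11 or 21 percentage points of power at 83 per arm (72% to 61% or 51%), and about 11 or 20 points at 62 completers (60% to 49% or 40%). Two limits apply: visit samples can support point prevalence at that visit, but they cannot verify abstinence in the intervals between visits; and nothing here calls the primary CPD test invalid.

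**What to change.** Amend section 12.0 as follows.

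1. **Point prevalence.** Define end-of-study 7-day point prevalence abstinence as no smoking by diary/TLFB together with CO ≤ 5 ppm and cotinine ≤ 15 ng/ml at the 6-month visit. For participants who report other nicotine products, use CO alone.
2. **Continuous abstinence.** Require no smoking by diary/TLFB and no failed cutoff at any attended follow-up visit, with the same rule for other nicotine products. State that the samples do not verify the intervals between visits.
3. **Missing samples.** Extend the multiple imputation that section 12.0 already plans for missing follow-up data. Show missing counted as smoking as a sensitivity analysis; it is one convention among several and could itself bias the comparison if sample return differs by arm.
4. **Self-report versions.** Report both outcomes by diary/TLFB only as supportive results.
5. **Support for CPD.** Add a mixed model of CO, and of log cotinine, over the six follow-up visits, labelled as supportive, in line with the R21 comparison of CO.

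The cost is a paragraph of wording and a little extra analysis; no new samples or visits are needed. The downside is somewhat lower abstinence rates.

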### **13.0 Provisions to Monitor the Data to Ensure the Safety of Subjects**

The PI ([name].) will be responsible for monitoring the trial. Questionnaires and interviews are all non-invasive and, as such, involve minimal physical risk to participants. However, adverse events will be monitored throughout the study and all events will be followed to resolution or stabilization. AEs will be coded on a weekly basis using Medical Dictionary for Regulatory Activities (MedDRA) rules and entered into a database. For each weekly study meeting, the research staff will prepare a summary of all AEs. The PI will review this at the weekly study meeting (or before if more urgent). Serious adverse events (SAEs) are defined as events, related or unrelated, that require or prolong hospitalization or result in congenital defects, death, disability, cancer, overdose, development of drug dependency or abuse, or any other life threatening event. The Institutional Review Board (IRB) of the Medical University of South Carolina (MUSC) will be immediately informed orally of an SAE as soon as the investigator, co-investigators, or study staff are made aware of it. A written report will be filed within 72 hours to the IRB, the NIDA Project Officer through the NIDA Serious Adverse Event Tracking and Reporting System (SAETRS). As further clinical information is obtained, follow-up and final SAE reports will be filed with the IRB and NIDA. The research staff will be instructed not to reveal whether a person is a participant in the study and will report to the PI any outside requests for information about a participant or any breaches in confidentiality. All requests by participants' physicians and other medical providers will be referred directly to the PI.

Additionally, a Data and Safety Monitoring Board (DSMB) will be created to ensure the safety of participants and the validity and integrity of data collected during the tenure of the project. The board will consist of a physician, a clinical psychologist, a statistician and a Pharm.D. or Nurse practitioner. This multidisciplinary group has extensive experience with management and monitoring of clinical research involving cue reactivity/exposure. The board will meet as needed to review the adverse events related to the study, and recommendations for appropriate action to maintain a favorable safety profile will be made. The board will also ensure that all serious adverse events have been followed to resolution, and that the appropriate agencies (including the IRB and federal funding agency) have been informed of the event.

All serious adverse events will be reported to the MUSC Institutional Review Board (IRB) within 24 hrs. Follow-up of all serious adverse events will be reported as well. All adverse events are reviewed weekly by the PI and yearly by both the DSMB and the IRB. Any significant actions taken by the local IRB, including significant protocol changes, will be relayed to NIDA. We anticipate the serious adverse event rate to be extremely low. If monitoring indicates otherwise, we will convene a special meeting of the DSMB.

### **15.0 Risks to Subjects**

Questionnaires and interviews are all non-invasive and, as such, involve minimal physical risk to the participants. Potential risks incurred by participants include:

- a) Loss of confidentiality: There is a risk of loss of confidentiality regarding the information obtained during study participation. Safeguards to protect confidentiality include locked records and firewalls around password-protected electronic data, and all study data being coded, with the key linking the code with a participant's identity being kept in a separate, locked file. Similar safeguards are followed for storage and processing of MRI data. MRI data is stored on secure storage owned by the Center for Biomedical Imaging (CBI). CBI

has a longstanding policy of reviewing all scans that are transferred to the laboratory from the MRI scanners, and assuring that all participant identifiers are removed, both from the scan image itself but also the electronic headers of the scan. The MRI scans are identified only by participant code, study code, and date of acquisition.

- b) Craving induction via cue reactivity/exposure: There is risk of increased craving for cigarettes or distress because of the cue-reactivity procedures. Craving may be pronounced during the intervention/24-hr test phase of the study.
- c) Magnetic Resonance Imaging: Although this procedure is generally low-risk, there are some concerns. Individuals will be screened for the presence of implanted metal (including but not limited to medical devices, shrapnel, tattoos or permanent makeup); those who screen positive will be excluded from the fMRI component of the study. Some participants may feel uncomfortable or confined once positioned within the bore of the MRI system. This potential reaction is reduced by discussing the procedure prior to entry into the magnet room and by communicating with the participant regularly over the intercom. Most importantly, participants will be exposed to the scanning environment through the use of a mock scanner. During the fMRI, participants will have voice contact with a radiology technician, and may request the scan be stopped at any time. If a participant expresses discomfort in the scanner and expresses an interest in terminating the scanning procedures, the imaging procedure will be terminated and the participant will be removed from the magnet.
- d) Incidental Findings: Magnetic Resonance Imaging: Another risk is the occurrence of incidental findings on MRI, such as risk of previously unrecognized stroke, hematomas, or other findings. All scans are reviewed at time of acquisition. Should any concerning findings be seen, we will obtain a consultation from a clinical neuro-radiologist who will provide an opinion on the significance of the finding and recommendations for further evaluation. [name] will contact the participant in question, convey these findings and recommendations, and facilitate referrals for further evaluation and treatment as needed.
- e) Adverse events unrelated to study participation may occur during the course of study participation.

There are no alternative methods of obtaining this information.

Drs. [name] and/or [name] will monitor all study participants for general psychological well-being/stability. The instrumentation to be used for physiological recordings meets all safety standards for non-invasive recordings, and participants will be located out of reach of any AC-powered devices in the laboratory. All laboratory sessions will be conducted under the supervision of experienced personnel at either the Addictive Behaviors Research Laboratory (ABRL) or the Translational Research of Addiction and Integrative Neuroscience (TRAIN) Laboratory. If crisis intervention is necessary, senior staff ([name]/[name]) will be available to evaluate the participant and provide an intervention or referral. All participants will be fully informed that they may withdraw from the experiment at any time without penalty.

To ensure confidentiality, participant data will be number coded, and only the investigators will have access to the master list of codes and participant names. All participant records will be kept in a locked file cabinet in an office that will be locked at times when not in use. All research staff undergo rigorous training on the ethical treatment of human subjects in research and receive continuous feedback about the need to maintain confidentiality.

## **16.0 Potential Benefits to Subjects or Others**

Benefits of study participation include detailed assessment of smoking and other substance use, potential reductions in craving to smoke and other reactions to smoking cues, reductions in smoking, abstinence from smoking and referral for additional treatment out side the context of study participation. Also, regular contact with and monitoring by research staff may serve to motivate participants in future attempts to abstain from cigarette use. Overall, given the potential benefits, it would appear that exposure to the risks associated with study participation are well justified. The risk/benefit ratio appears to favor the study participant.

